### **VISIT 2 (occurring within 1 month after Visit 1)**

Step 1: The subject will arrive at the remote location site.

Step 2: This session will be assisted by a trained facilitator. The subject will be programmed by the remotely located primary audiologist. This program will be saved in Program slot #2, and the cdx file will be anonymized and exported to the sponsor.

Step 3: The subject will complete the Remote Programming Satisfaction Survey.

Step 4: The subject will use this Facilitated MAP at home for 2-4 weeks.

### **VISIT 3 (2-4 weeks after Visit 2)**

Step 1: The subject will return to his/her primary programming center.

Step 2: Speech perception testing will be completed using the Facilitated MAP (Program 2).

Step 3: The Subject will complete the SSQ-C comparing the familiar MAP and the Facilitated MAP.

### **VISIT 4 (2-4 weeks after Visit 3)**

Step 1: The subject will arrive at the remote location site.

Step 2: This session will be conducted with the subject acting and his/her own facilitator. The subject will be programmed by the remotely located audiologist. This

program will be saved in Program slot #2 (taking the place of the previous MAP in that slot), and the cdx file will be anonymized and exported to the sponsor.

Step 3: The subject will complete the Remote Programming Satisfaction Survey.

[figure not shown]
Step 4: The subject will use this Self MAP at home for 2-4 weeks.

#### **VISIT 5 (2-4 weeks after Visit 4)**

Step 1: The subject will return to his/her primary programming center.

Step 2: Speech perception testing will be completed using the Self MAP (Program 2).

Step 3: The subject will complete the SSQ-C (comparing the familiar MAP and the Self MAP), and the Telemedicine Experience Questionnaire.

**Figure 2: Study visit flow chart**

## Endpoint Testing

**Primary Safety Endpoint: Characterize the safety profile of device and/or procedure related adverse events associated with facilitated remote MAP programming, unassisted MAP programming and audiologist live MAP programming**

Safety Endpoint testing will occur at Visit 2 and Visit 4.

- Recipients will be MAPped via telecommunication by a remotely located audiologist.
- Any adverse events associated with the MAPping will be recorded on the New Adverse Event Reporting Form. Any AEs identified at Visit 2 or Visit 4 will be re-evaluated at subsequent visits and updated on the Follow Up Adverse Event Reporting Form.

**Co-Primary Efficacy Endpoint 1: Demonstrate that performance on CNC words using a remotely programmed facilitated MAP is no worse than when using a live programmed MAP**

Efficacy Endpoint 1 testing will occur at Visit 1 and Visit 3.

- **Visit 1:** Speech perception scores will be obtained in Program 1 (familiar/Live)
- **Visit 3:** Speech perception scores will be obtained in Program 2 (Facilitated MAP)

**Co-Primary Efficacy Endpoint 2: Demonstrate that performance on CNC words using an unassisted remotely programmed MAP is no worse than when using a live programmed MAP**

Efficacy Endpoint 2 testing will occur at Visit 1 and Visit 5.

- **Visit 1:** Speech perception scores will be obtained in Program 1 (familiar/Live)
- **Visit 5:** Speech perception scores will be obtained in Program 2 (Self MAP)

**Secondary Efficacy Endpoint: Demonstrate non-inferiority of unassisted remote MAP programming compared to facilitated MAP programming via performance on CNC words.**

Efficacy Endpoint 2 testing will occur at Visit 3 and Visit 5.

- **Visit 3:** Speech perception scores will be obtained in Program 2 (Facilitated MAP)
- **Visit 5:** Speech perception scores will be obtained in Program 2 (Self MAP)

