### ADVERSE DEVICE EFFECTS

To monitor subject safety throughout this IDE study, any procedure or device related adverse events will be recorded. Information on all adverse events will be maintained by event type. The investigator will complete an Adverse Event form if any adverse event is reported or observed for a subject during this IDE, even if they were acknowledged as risk factors in the Informed Consent form.

Adverse device effects refer to any undesirable clinical or medical occurrence associated with use of the device or participation in the study. Any/all adverse device effects are to be recorded via the Adverse Event form. Adverse device effects will be reported if observed, even if they were acknowledged as risk factors in the Informed Consent form.

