10.1.1 Safety Endpoint

The objective of the safety analysis is to characterize the safety profile of device and/or procedure related adverse events associated with facilitated remote MAP programming, unassisted MAP programming and audiologist live MAP programming.

All Adverse Events will be tabulated according to the study interval, the number of procedure-related events, and the number of device-related events. Procedure- and device-related adverse events will be summarized as rates, where the numerator for each rate will be the number of subjects with at least one procedure- or device-related event, and the denominator will be the total number of subjects.

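### Scheduled safety testing is stated only for the two remote programming days, so home-use events rely on passive reporting, and the SAP's rates are not split by programming method

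*Protocol*

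**What the plan says.** The primary safety endpoint is a profile of device- and procedure-related adverse events under three methods: facilitated remote, unassisted remote and live programming (protocol Study Summary and Endpoint Testing; SAP 10.1.1).

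**Schedule.** Endpoint Testing states "Safety Endpoint testing will occur at Visit 2 and Visit 4". For later visits it adds "Any AEs identified at Visit 2 or Visit 4 will be re-evaluated at subsequent visits and updated on the Follow Up Adverse Event Reporting Form".

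**Exposure.** After the Visit 2 session, "The subject will use this Facilitated MAP at home for 2-4 weeks". After the Visit 4 session, "The subject will use this Self MAP at home for 2-4 weeks". The Facilitated MAP stays in slot #2 until it is overwritten at Visit 4, and the familiar MAP stays in slot #1 throughout (MAP Programming Methods).

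**Study-wide recording.** The Adverse Device Effects section says "To monitor subject safety throughout this IDE study, any procedure or device related adverse events will be recorded", and "The investigator will complete an Adverse Event form if any adverse event is reported or observed for a subject during this IDE".

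**Analysis.** SAP 10.1 counts adverse events whatever their onset. SAP 10.1.1 says "All Adverse Events will be tabulated according to the study interval", then gives rates of subjects with at least one procedure- or device-related event, divided by all subjects.

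**The concern.** A MAP's effects can appear in the session in which it is made or in the weeks when it is worn. The stated schedule looks at the first occasion. At later visits it commits only to following up events already identified in those sessions. Visits 3 and 5 come straight after home use, yet their listed steps are speech testing and questionnaires, with no enquiry about new events.

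Two things are at stake. One is ascertainment: an event that the subject does not volunteer and the clinic does not notice is never recorded. The other is attribution: the endpoint asks for a profile by method, and the Introduction promises a comparison of live and remote adverse events, but the SAP has no rule for placing an event under a method and no rate per method.

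**Working it through.** There is no safety figure in the plan to reproduce. The only calculated figure, a minimum of 26 evaluable subjects, is for CNC word recognition and does not bear on this point.

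**1. Time at risk against scheduled testing.** Inputs are the visit windows in the Study Summary.
- Facilitated MAP, Visit 2 to Visit 4: (2-4 weeks) + (2-4 weeks) = 4-8 weeks.
- Self MAP, Visit 4 to Visit 5: 2-4 weeks.
- Total, Visit 2 to Visit 5: 6-12 weeks, or 42-84 days.
- Share taken by the two programming days: 2/84 = 2.4% to 2/42 = 4.8%.

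**2. What each method receives.**

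| Period | MAP under study | Scheduled safety testing at or after the end of home use |
|---|---|---|
| Visit 1 to 2 | Familiar (previously live-programmed) | Visit 2, which is also the Facilitated session |
| Visit 2 to 4 | Facilitated | Visit 4, which is also the Self session |
| Visit 4 to 5 | Self | None stated |

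At Visits 2 and 4 nothing separates events from the period just ended from events of the session that day. The live row holds no live session: the Visit 1 steps state that no programming is done.

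**3. From recorded event to reported rate.** A recorded home-use event is counted (SAP 10.1) and tabulated by study interval (SAP 10.1.1). The visit order is fixed, so intervals could be matched to MAPs. But the SAP does not define the intervals, and the rates carry no split by method. Dates alone would not settle which program was in use, because slot #1 remains available.

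**4. Illustration of under-capture.** The documents give no event rate or capture fraction, so both are assumed. With event proportion p, capture fraction c and 40 subjects, P(at least one recorded) = 1 − (1 − pc)^40.

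| Assumed p | c = 1 | c = 0.5 | c = 0.25 |
|---|---|---|---|
| 5% | 1 − 0.95^40 = 87% | 1 − 0.975^40 = 64% | 1 − 0.9875^40 = 40% |
| 2% | 1 − 0.98^40 = 55% | 1 − 0.99^40 = 33% | 1 − 0.995^40 = 18% |

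Even with full capture, zero events in 40 subjects leaves a one-sided 95% upper bound of 1 − 0.05^(1/40) = 7.2%. Incomplete capture weakens that statement further.

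**The case against.** The best defence is that scheduled testing and study-wide recording add to each other. Endpoint Testing names two visits without saying that events found elsewhere are excluded, the Adverse Device Effects section covers the whole study, and the SAP counts events whatever their onset. This stands, and it rules out three stronger readings that a reader might infer:

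- That safety is assessed only on the two programming days. It is *scheduled* only then; recording runs throughout.
- That home-use events fall outside the endpoint. Once recorded, they are in the tabulation and the rates.
- That the protocol sections contradict each other. They can be read together; what is missing is a statement of how they fit.

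The silence of Table 1 is also weak evidence. It lists speech tests and questionnaires and has no adverse event row at any visit, including Visits 2 and 4, where recording is required. The Visit 2 and Visit 4 steps list none either. Figure 2, the visit flow chart, is not shown in the text available, so an adverse event step there cannot be ruled out. Subjects do return to their own clinic at Visits 3 and 5, and the Visit 5 questionnaire allows open comments.

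None of this supplies a question about new events after home use, and counting rules act only on events that have been found. Nor does the fixed visit order replace a rate per method.

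**Conclusion.** The point holds as a gap in scheduled ascertainment and in reporting by method. Followed as written, the plan leaves new events over the 6-12 weeks from Visit 2 to Visit 5 to passive reporting, apart from what surfaces at Visit 4. It states no safety assessment after home use of the Self MAP, and its rates do not deliver the by-method profile that the endpoint names.

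A reader might go further and conclude that remote programming will look safer than live. The documents do not support that: there is no live session to compare with, no event rate is given, and passive reporting lowers absolute counts without a shown difference between methods. The size of any undercount cannot be stated; the percentages above illustrate assumed values only. The conclusion rests on the written visit steps and Endpoint Testing text, with Figure 2 unseen. This merits a change but does not invalidate the design.

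**What to change.** **Protocol, Endpoint Testing.** Extend safety endpoint testing to Visits 3 and 5 with a standard adverse event question. Ask it also at Visit 2 before programming, to cover the familiar-MAP period, and at Visit 4 before programming, to close the Facilitated period. Record the onset date and the program slot in use at onset. Add the question to the visit steps and a matching row to Table 1, and state how this schedule relates to the study-wide recording under Adverse Device Effects.

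**SAP 10.1.1.** Define the intervals as Visit 1-2 (familiar MAP), Visit 2-4 (Facilitated) and Visit 4-5 (Self). Report subject-level rates per method, and show interval length or exposure beside each, because the Facilitated interval (4-8 weeks) is twice the Self interval (2-4 weeks). State that the Visit 1-2 period reflects use of a MAP programmed live beforehand, not a live programming session.

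**Cost.** Wording changes in two documents, one form field each for onset date and slot, and one question at visits that already take place. Reported event rates may rise slightly because events are now asked about.

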### Test Materials:

- CNC word list presented at 60 dBA (subject facing speaker) with contralateral ear plugged. Two lists (of 50 words each) will be completed for each condition. Score each test condition for % of words correct.

**Note:** The test material lists will be randomized.

**Table 1: Summary of data collection visits**

Test Material and Condition	Visit 1	Visit 2	Visit 3	Visit 4	Visit 5
CNC words in Program 1 (original/Live program)	X				
CNC words in Program 2 (remote program)			X		X
Remote Programming Satisfaction Survey		X		X	
SSQ-C			X		X
Telemedicine Experience Questionnaire					X

### MAP Analysis:

Anonymized Live MAP, Remote Facilitated MAP, and Remote Self MAP cdx files will be submitted by the audiologist to the sponsor for analysis of electrical charge data.

### ADVERSE DEVICE EFFECTS

To monitor subject safety throughout this IDE study, any procedure or device related adverse events will be recorded. Information on all adverse events will be maintained by event type. The investigator will complete an Adverse Event form if any adverse event is reported or observed for a subject during this IDE, even if they were acknowledged as risk factors in the Informed Consent form.

Adverse device effects refer to any undesirable clinical or medical occurrence associated with use of the device or participation in the study. Any/all adverse device effects are to be recorded via the Adverse Event form. Adverse device effects will be reported if observed, even if they were acknowledged as risk factors in the Informed Consent form.

## UNANTICIPATED ADVERSE DEVICE EFFECTS

Unanticipated adverse device effects refer to any event not identified above that represents a “serious adverse effect on health or safety or any life-threatening problem or death caused by, or associated with, a device if that effect, problem or death was not previously identified in nature, severity, or degree of incidence in the investigational plan or application, or any other unanticipated serious problem associated with a device that relates to the rights, safety, or welfare of subjects.” [FDA 21 CFR 812.3(s)]

Investigators are to inform their respective Institutional Review Boards (IRBs) and Cochlear Americas immediately if an unanticipated adverse device effect is suspected (no more than 10 working days after the investigator learns of the effect). If the case is determined to be an unanticipated adverse device effect, the investigator will fill out an “Unanticipated Adverse Device Effect Form.” Cochlear Americas will report the results of an evaluation of the unanticipated adverse device effect to the FDA and all other reviewing IRBs and investigators within 10 working days after first receiving notice of the event.

## DATA ANALYSES

### Sample Size

Based on the variability observed in earlier studies, it was determined using PASS (NCSS Statistical Software) that a minimum of 26 subjects would provide at least 90% power for hypothesis testing of the two co-primary endpoints at the 0.025 alpha level.

The planned sample size of 40 subjects will provide adequate power for hypothesis testing of the two coprimary endpoints at the 0.025 alpha level. The following general assumptions have been made:

- T-tests of difference scores to test for non-inferiority with a non-inferiority margin of 10% for CNC word recognition
- One-sided 0.025 alpha level
- Assumed distribution for population (standard deviation)
- Desire for 90% power

The power analyses for the primary test metrics are provided below.

[Table 2: Sample size calculation for CNC word recognition](#)

Scenario (Non-inferiority)	Minimum Evaluable Sample Size Required
One-sided 0.025 alpha, 90% power, SD = 15%, NIM = 10%, true difference = 0	26

## **Additional Statistical Analyses**

Statistical Analysis for this study is addressed in detail in the document entitled “Statistical Analysis Plan: Use of telemedicine in the remote programming of Nucleus® cochlear implants.”

## **STUDY REPORT AND PUBLICATION**

A description of this clinical trial will be available on <http://www.ClinicalTrials.gov>, as required by U.S. Law.

The aggregate data resulting from this study will be the proprietary information of the Sponsor and may be made public after all data have been analyzed and the study results are available. None of the data resulting from this study will be allowed to be presented or published in any form, by the Investigator or any other person, without the prior written approval of the Sponsor. At the end of the study, a clinical study report will be written by the Investigators or their designee and reviewed by the Sponsor.

1 PURPOSE

This statistical analysis plan (SAP) describes the statistical methods to be used during the reporting and analysis of data collected under the Cochlear IDE Study titled, “Safety and Efficacy of Remote Programming of Nucleus Cochlear Implants.”

2 SCOPE

This SAP should be read in conjunction with the study protocol. This version of the plan has been developed with respect to the Cochlear IDE Study protocol version 1.0, dated 03-Aug-2015. Any further changes to the protocol may necessitate updates to the SAP.

3 APPLICABLE DOCUMENTS

Document Number	Document Title
	Cochlear IDE Protocol Version 1.0 (03Aug2015)
STATSOP-002	Statistics Standard Operating Procedure – Statistical Analysis Plan

4 SOFTWARE

All statistical analyses will be completed using SAS software (SAS Institute, Inc., SAS Campus Drive, Cary, NC 27513, USA.) In the event an analysis is required that is better suited for a statistical package other than SAS, another package (e.g. R) will be used.

5 ABBREVIATIONS AND DEFINITIONS

Abbreviation / Term	Definition
ADE	Adverse Device Effect - any untoward and unintended response to an investigational medical device
AE	Adverse Event - any untoward medical occurrence in a subject
CI	Cochlear Implant
CRF	Case Report Form
eCRF	Electronic Case Report Form
Enrolled	A subject is enrolled when he/she meets all inclusion/exclusion criteria and signs the informed consent form
Facilitator	A trained staff member at the programming site
IDE	Investigation Device Exemption
Live Programming	Traditional face to face programming interaction between a recipient and an audiologist at the same physical location
MAP	A program that defines the individualized parameters of recipients for a specific speech coding strategy
Remote Programming	A programming interaction between a recipient and an audiologist that occurs via telecommunication technology when the two parties are at different physical locations
SAE	Serious Adverse Event – an adverse event that: 
• Led to death• Led to a serious deterioration in the health of the subject, that

	
either resulted in a life-threatening illness or injury, or a permanent impairment of a body structure or a body function, or in-patient hospitalization or prolongation of existing hospitalization, or resulted in medical or surgical intervention to prevent life-threatening illness or injury or permanent impairment to a body structure or a body function
 
 • Led to fetal distress, fetal death or a congenital abnormality or birth defect
SAP	Statistical Analysis Plan

6 STUDY OBJECTIVES

The purpose of this study is to characterize the safety and demonstrate the efficacy of CI programming via telecommunication.

7 STUDY POPULATION

The study population will include up to 40 subjects (12 years of age or older) who have unilateral or bilateral cochlear implants and are capable of completing the study evaluation.

8 SAMPLE SIZE

Based on the variability observed in earlier studies, it was determined using PASS (NCSS Statistical Software) that a minimum of 26 subjects would provide at least 90% power for hypothesis testing of the two co-primary endpoints at the 0.025 alpha level.

The planned sample size of 40 subjects will provide adequate power for hypothesis testing of the two co-primary endpoints at the 0.025 alpha level. The following general assumptions have been made:

- Paired T-tests of difference scores to test for non-inferiority with a non-inferiority margin of 10% for CNC word recognition
- One-sided 0.025 alpha level
- Assumed distribution for population (standard deviation)
- Desire for 90% power

The power analyses for the primary test metrics are provided below.

Sample size calculation for CNC word recognition:

Scenario (Non-inferiority)	Minimum Evaluable Sample Size Required
One-sided 0.025 alpha, 90% power, SD = 15%, NIM = 10% , true difference = 0	26

More subjects will provide additional power or a similar degree of power for more conservative assumptions. Because the non-inferiority sample size calculation assumes a true difference of 0 between remote and live MAP programming, we propose a sample size of 40 subjects to allow for:

1. the possibility that variability will be greater than expected,
2. the possibility that the true difference may be greater than 0, and
3. the possibility of subject attrition.

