11 TYPE 1 ERROR CONTROL

Study success will be defined by rejection of the null hypotheses in the comparison of facilitated remote MAP programming via telecommunication to live MAP programming and/or the rejection of the null hypothesis in the comparison of unassisted remote MAP programming via telecommunication to live MAP programming for CNC word recognition. Because study success is based on two separate endpoints, type I error will be maintained at an overall one-sided alpha level of 0.025. The secondary efficacy objective will be tested only in the event both co-primary efficacy objectives are met. Thereby preserving the overall 0.025 alpha level

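### Does the 90% power quoted at 26 subjects overstate the trial's power, given that it is the power of one co-primary endpoint and not of both?

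*SAP*

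**What the plan says.** The protocol (Data Analyses, Sample Size) and SAP section 8 make the same statement: "a minimum of 26 subjects would provide at least 90% power for hypothesis testing of the two co-primary endpoints at the 0.025 alpha level". The basis listed in the SAP is "Paired T-tests of difference scores to test for non-inferiority with a non-inferiority margin of 10% for CNC word recognition", together with "One-sided 0.025 alpha level" and "Desire for 90% power". The table has one row, "One-sided 0.025 alpha, 90% power, SD = 15%, NIM = 10% , true difference = 0", with 26 as the evaluable minimum. Neither document gives a correlation between the two difference scores or a joint power.

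Both documents then plan for more than the minimum: "The planned sample size of 40 subjects will provide adequate power for hypothesis testing of the two co-primary endpoints". SAP section 8 explains the margin above 26 by greater variability than expected, a true difference above zero, and "the possibility of subject attrition".

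SAP section 11 defines study success as rejecting the null hypothesis for the facilitated comparison, the unassisted comparison, or both. It requires both in one place only: "The secondary efficacy objective will be tested only in the event both co-primary efficacy objectives are met".

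**The concern.** The power sentence names two endpoints and gives one percentage. The endpoints are called co-primary, a term often taken to mean that both must succeed, so 90% can be read as the probability of winning on both. The calculation shown covers a single comparison, and joint power is necessarily lower than the power of either test alone unless the two outcomes always agree.

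If 26 were treated as enough for both claims, the sponsor could tolerate a loss of 14 of the 40 subjects in the belief that 90% power remained. The chance of reaching the secondary endpoint would also be lower than supposed, since that test opens only when both primary comparisons succeed.

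**Working it through.** **Inputs.** From SAP section 8: one-sided alpha 0.025, SD of the within-subject difference 15 points, margin 10 points, true difference 0, paired t-test. From SAP 10.2: the two differences are Live minus Facilitated and Live minus Unassisted, so they share the Live score.

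**Assumption.** The correlation ρ of the two differences is not stated. If the three scores have equal variance σ² and equal pairwise correlation r, each difference has variance 2σ²(1 − r) and their covariance is σ²(1 − r), so ρ = 0.5. I use 0.5 as the central value and 0 to 0.9 as the range.

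**1. The plan's own figure.** Power = P(T > t₀.₉₇₅,ₙ₋₁), where T is noncentral t with n − 1 degrees of freedom and noncentrality 10/(15/√n).

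- n = 25: noncentrality 10/(15/5) = 3.33, power 89.2%.
- n = 26: noncentrality 10/(15/5.099) = 3.40, power 90.4%.

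So 26 reproduces exactly as the minimum for one endpoint.

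**2. Both endpoints, and at least one, each tested at 0.025.** Bivariate normal differences, 200,000 simulated trials per setting. At ρ = 0 the closed forms are 0.9043² = 81.8% for both and 1 − (1 − 0.9043)² = 99.1% for at least one.

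| n | ρ | Both | At least one |
|---|---|---|---|
| 26 | 0 | 81.8% | 99.1% |
| 26 | 0.5 | 83.8% | 97.1% |
| 26 | 0.9 | 87.4% | 93.6% |
| 40 | 0 | 96.9% | >99.9% |
| 40 | 0.5 | 97.1% | 99.8% |
| 40 | 0.9 | 97.7% | 99.1% |

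At n = 40 the power of one endpoint is 98.4%.

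**3. Number needed for 90% on both.** At ρ = 0.5, 30 subjects give just under 90% and 31 give about 91%. At ρ = 0, 31 give 0.9485² = 89.97% and 32 give 0.9547² = 91.1%. So 31 or 32 evaluable subjects suffice. From 40, that allows a loss of 8 or 9 subjects (20% to 22.5%). A fall to 26 would be a loss of 14/40 = 35%.

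**4. If alpha were split to 0.0125 per test.** At n = 26, power is 83.8% per endpoint and about 94% for at least one at ρ = 0.5 (97% at 0, 88% at 0.9). At n = 40 it is 96.7% per endpoint. The 83.8% per endpoint here matches the joint figure in step 2 by coincidence; they are different quantities.

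**5. Would 31 belong in the table?** For the criterion in that row (one-sided 0.025, 90% power, one comparison), 31 subjects give 94.9%. The minimum for that criterion is 26, so replacing it with 31 would make a correct row wrong.

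**The case for a change.** The strongest counter-argument is that planning for 40 does not wholly dispose of the matter. The SAP holds the extra subjects against larger variability, a non-zero difference and attrition, so some of the surplus may already be spent. As illustrations, with all 40 evaluable and ρ = 0.5:

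- A true difference of 2 points with SD 15 gives 90.8% per endpoint and about 84% for both.
- An SD of 18 with no true difference gives 92.9% per endpoint and about 88% for both.

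These figures are right, and they show that joint power falls below 90% sooner than per-endpoint power does. They rest on departures from the stated assumptions, however, and at this central correlation power for at least one endpoint stays at about 97% or higher in both cases. They bear on the chance of reaching the secondary endpoint, for which the plan makes no power claim.

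It also stands that the wording is loose, and that calling the endpoints co-primary sits awkwardly with a success rule that either can satisfy. Testing each at 0.025 under that rule does not hold an overall 0.025: the chance of at least one false success is about 4.5% at ρ = 0.5 when both true differences equal the margin. That is a separate question of type I error control, and rewording the power statement would not settle it.

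**Conclusion.** No change to the plan is needed. The 90% at 26 subjects is a correct per-endpoint power, and the basis shown beside it (paired t-tests and a single-comparison table row) is enough for a statistician to read it that way. For study success as SAP section 11 defines it, 26 subjects give about 94% to 99% with each test at 0.025, so the claim of at least 90% also holds for that event. The lower figure of about 82% to 87% applies only to meeting both endpoints, which the plan requires solely before the secondary test.

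At the planned 40 subjects, power to meet both is about 97%, and it stays at or above 90% down to 31 or 32 evaluable subjects. These results assume SD 15, zero true difference and a correlation between 0 and 0.9. Inserting the words each of before the two endpoints would make the sentence clearer, but enrolment, analysis and conclusions would be the same with or without it.
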